#### Thromboembolic episodes

There is a risk of thrombosis when patients with congenital fibrinogen deficiency are treated with human fibrinogen particularly with high dose or repeated dosing (Core SmPC for Human Fibrinogen Products, 2009/2015]; (de Moerloose et al. 2010, EMA (Committee for Medicinal Products for Human Use) 2015). Thus, patients given human fibrinogen should be observed closely for signs or symptoms of thrombosis.

Prothrombin fragments  $F_{1+2}$ , TAT, and D-dimer are monitored regularly to detect a hypercoagulable status.

An (transient) increase in body temperature may occur (Core SmPC for Human Fibrinogen Products, 2009/2015).

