# Follow-up Day 1 (24 h Post-End of Infusion)

The patient will be hospitalized.

- Coagulation activation: PT(INR), aPTT, TAT, F1+2, D-dimer, to be done *locally or centrally* (depending on local availability of validated test systems)
- Safety laboratory: to be done locally
  - ⇒ Hematology (RBC, WBC, platelet count, hemoglobin, hematocrit)
  - Biochemistry (ASAT, ALAT, γ-GT, AP, total bilirubin, creatinine, urea, potassium, sodium, calcium, and chloride)
  - ⇒ Urine analysis (pH, blood, WBC, protein, glucose, ketone bodies, nitrite, bilirubin, urobilinogen)
    - o in Adults (18 75 years) and Children/Adolescents Group I and Group II (≥ 6 years): as required, but at least to be done once after last infusion of BT524 and before discharge
    - Pre-school Children Group III (2 to < 6 years): 24 h post end of last infusion
    - Newborns/Infants and Toddlers Group IV (0 days to < 2 years): 24 h post end of last infusion
- Ultrasonography of lower limbs (according to study specific ultrasonography manual) and of any other suspected site: whenever a thrombosis or TEE is suspected
- Vital signs (pulse, blood pressure, body temperature)
- Physical examination
- Adverse events
- Concomitant disease / concomitant medication
- Assessment of risk and burden (paediatric patients)

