11.8 Clinical safety laboratory

All safety lab values will be re-calculated to SI units before further processing.

The following statistical analyses will be presented for part I (SAF) and on event level from part II for FBE (separated by ODP/ODT, hospitalization, age group as appropriate) per lab test (as listed subsequently). Note that 'baseline' refers to the pre-dose measurement within each observation period of the indication/event:

1. Quantitative data will be examined for trends using descriptive statistics (number of patients/events with data, number of patients/events with missing values, mean, SD, median, minimum, and maximum) of measured values at baseline and each planned post-baseline visit over time.
2. Qualitative data based on laboratory specific normal ranges will be categorized according to the categories (e.g. below normal/normal/above normal) and presented as number and relative frequency of patients (and/or events).
3. Number and percentages of patients/events with on treatment values considered as clinically significant (CS) by the investigator will be tabulated (across planned visits). Out of range values not assessed for clinical significance are not included in the analysis and are provided in Listing.

Note that in the listings, laboratory values that are outside the normal range will additionally be flagged. Any out-of-range values that are identified by the investigator as being clinically significant will also be shown in an extra data listing. Additionally, a separate listing showing the normal ranges will be generated.

Hematology and clinical chemistry

Hematology tests include RBC, WBC, platelet count, hemoglobin, and hematocrit (all quantitatively).

Biochemistry tests measure aspartate aminotransferase, alanine aminotransferase, γ -glutamyltransferase, alkaline phosphatase, total bilirubin, creatinine, urea, potassium, sodium, calcium, chloride (all quantitatively).

Urinalysis

Blood, leukocytes, protein, glucose, ketones, nitrite, bilirubin, urobilinogen were measured only qualitative, pH was measured quantitative. For the analysis only qualitative results will be used (for pH the normal ranges are used for classification of results into "normal", "abnormal"). Frequencies and percentages of normal and abnormal values will be presented. The quantitative results will only included in the listings.

Markers of coagulation activation

Coagulation activation parameters include PT, PT(INR), aPTT, TAT, F1+2, D-dimer.

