Measurements of coagulation activation parameters from additional samplings (beside pre-defined timepoints) taken as required per investigator will be listed and not used in the analyses.

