Listing	16.16.2	Physical Examination - Investigator Clinically Significant Findings – SAF I
Listing	16.16.3	Physical Examination – FBE
Listing	16.16.4	Physical Examination - Investigator Clinically Significant Findings – FBE
Fibrinogen Inhibitory Antibodies		
Table	14.3.4.5.1	Fibrinogen Inhibitory Antibodies Data: Frequencies and Percentages of Patients by Time Point – SAF I
Table	14.3.4.5.2	Fibrinogen Inhibitory Antibodies Data: Frequencies and Percentages of Patients by Time Point – SAF II
Table	14.3.4.5.3	Fibrinogen Inhibitory Antibodies Data on Event Level: Frequencies and Percentages of Patients by Time Point – FBE
Listing	16.17.1	Fibrinogen Inhibitor Antibodies – SAF I
Listing	16.17.2	Fibrinogen Inhibitor Antibodies – FBE
Markers of coagulation activation		
Table	14.3.4.6.1	Coagulation Activation Data: Descriptive Statistics of PT, PT (INR), aPTT, TAT, F1+2, D-dimer by Time Point – SAF I
Table	14.3.4.6.2	Coagulation Activation Data: Frequencies and Percentages of clinically significant of PT, PT (INR), aPTT, TAT, F1+2, D-dimer by Time Point without Hospitalization – SAF I
Table	14.3.4.6.3	Coagulation Activation Data on Event Level: Descriptive Statistics of PT, PT (INR), aPTT, TAT, F1+2, D-dimer by Indication and Time Point – FBE
Table	14.3.4.6.4	Coagulation Activation Data on Event Level by Age Group: Descriptive Statistics of PT, PT (INR), aPTT, TAT, F1+2, D-dimer by Time Point – FBE
Table	14.3.4.6.5	Coagulation Activation Data on Event Level by Hospitalization: Descriptive Statistics of PT, PT (INR), aPTT, TAT, F1+2, D-dimer by Time Point – FBE
Table	14.3.4.6.6	Coagulation Activation Data on Event Level: Frequencies and Percentages of Clinically Significant PT, PT (INR), aPTT, TAT, F1+2, D-dimer by Indication and Time Point – FBE
Table	14.3.4.6.7	Coagulation Activation Data on Event Level by Age Group: Frequencies and Percentages of Clinically Significant PT, PT (INR), aPTT, TAT, F1+2, D-dimer by Time Point – FBE
Table	14.3.4.6.8	Coagulation Activation Data on Event Level by Hospitalization: Frequencies and Percentages of Clinically Significant PT, PT (INR), aPTT, TAT, F1+2, D-dimer by Time Point – FBE
Listing	16.18.1	Markers of coagulation activation – SAF I
Listing	16.18.2	Markers of coagulation activation assess as clinically significant by the investigator – SAF I
Listing	16.18.3	Markers of coagulation activation – FBE
Listing	16.18.4	Markers of coagulation activation assess as clinically significant by the investigator – FBE

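### As-required coagulation samples in hospitalised Part II events are kept out of the coagulation tables, so a per-event count of clinically significant marker values can only be too low

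*SAP*

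**What the plan says.** SAP 11.8 sets three rules that bear on this point.

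- Item 1: quantitative laboratory data are summarised "at baseline and each planned post-baseline visit over time".
- Item 3: patients or events with on-treatment "values considered as clinically significant (CS) by the investigator will be tabulated (across planned visits", which limits the count to scheduled assessments.
- Under the markers of coagulation activation (PT, PT(INR), aPTT, TAT, F1+2, D-dimer): measurements from samplings outside the pre-defined time points and "taken as required per investigator will be listed and not used in the analyses".

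The same section adds: "Any out-of-range values that are identified by the investigator as being clinically significant will also be shown in an extra data listing". The list of outputs in SAP 15.1 carries this through for Part II as Listing 16.18.4, "Markers of coagulation activation assess as clinically significant by the investigator". Listing 16.18.3 holds all coagulation values. Tables 14.3.4.6.3 to 14.3.4.6.8 give the Part II coagulation summaries and CS frequencies by time point, split by indication, age group and hospitalisation.

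On purpose, protocol 11.7 (Thromboembolic episodes) says that prothrombin fragments F1+2, "TAT, and D-dimer are monitored regularly to detect a hypercoagulable status".

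**The concern.** Restricting means by visit to planned samples is ordinary practice, because an unscheduled sample belongs to no visit. A safety count asks a different question: did this event show a clinically significant marker value at any time after the dose? For that question the time of the sample does not matter, and leaving samples out loses information.

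The markers concerned are the ones the protocol relies on to detect a hypercoagulable state, and protocol 11.7 says the risk of thrombosis is greatest with high or repeated dosing. Hospitalised Part II events are where repeated dosing is expected, and they are also where coagulation sampling is partly as required. A reader of the coagulation tables alone could conclude that no marker reached clinical significance when the listing shows otherwise.

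**Working it through.** There is no figure in the plan to reproduce. The check sets the sampling schedule beside the analysis rule.

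**Where as-required coagulation samples arise.** Part I and Part II events without hospitalisation have fixed coagulation time points, plus an optional visit in Part II. For Part II events with hospitalisation the schedule is as follows (protocol 13.1.2.4 unless stated):

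| Time | Aged 6 or over | Under 6 |
|---|---|---|
| Pre-dose | fixed | fixed |
| Day 0 after infusion | 1 h, plus as required | as required only |
| 24 h | fixed | fixed |
| Day 2 to day before discharge | as required | as required |
| Discharge day | fixed | fixed in the visit text; as required in flowcharts 3.4 and 3.5 |
| Optional visit | taken if the visit occurs | taken if the visit occurs |
| Safety visit | fixed | not taken |

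Protocol 14.5.1.3 gives the Part II coagulation schedule with no age split. It names the 1 h, discharge-day and safety-visit samples for everyone and refers to the flowcharts for time points.

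**What the rule does to a count.** For event i, let P = 1 if at least one planned post-dose sample is CS, and R = 1 if at least one as-required post-dose sample is CS. A count restricted to planned samples is the sum of P. A count over all post-dose samples is the sum of max(P, R). The difference is the sum of R × (1 − P), which is zero or positive for every event. So the restricted count is either right or too low. This concerns the count. SAP 5.1 bases percentages on events with data, so the denominator should be held fixed when the two counts are compared.

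**Size.** The number of as-required samples and the proportion rated CS are not in the documents. The difference cannot be estimated, even as a range.

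**Consistency with the rest of the plan.**

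- Protocol 15.2.6 classifies safety laboratory results as normal or abnormal and by clinical relevance. It sets no limit to planned visits, although it leaves details to the SAP.
- SAP 2.1 states that the analysis agrees with the protocol. For laboratory data it declares only that shift tables are dropped, so this restriction is not declared.
- SAP 11.10 (physical examination) puts a patient or event in the abnormal CS category if at least one post-baseline evaluation was abnormal and CS. That is the kind of count missing for coagulation.

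**The case against.** The strongest answer is that CS values are not lost. Protocol 14.5.2 requires an out-of-range value judged clinically relevant to be documented as an adverse event if it first occurs after BT524, and nothing there limits this to planned samples. Such events reach the TEAE tables (SAP 11.1), thrombosis has its own special-interest tables, and CS values are listed. A reader might therefore infer too much from the exclusion in thinking that these values cannot appear in any safety table; the documents do not support that.

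The adverse-event route still does not replace the count. It omits values that are only signs of an event already reported and values that are not a first occurrence (14.5.2). Protocol 14.6.2 prefers the clinical term to the laboratory term, so the marker may not be identifiable. SAP 4.1.2.2 analyses adverse events per patient, while the coagulation tables are per event.

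Four further objections stand, in whole or in part:

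- It is tempting to say that these samples are drawn because thrombosis is feared. No trigger is stated for them. Suspected thrombosis or TEE is the stated trigger for ultrasonography.
- It is tempting to apply the wording "as required, but at least to be done once after last infusion of BT524 and before discharge" to coagulation. In the Follow-up Day 1 schedule it governs haematology, biochemistry and urinalysis in patients aged 6 or over. Coagulation at 24 h is unconditional.
- It is tempting to say that every as-required sample is dropped, or that only pre-dose and 24 h samples remain under age 6. Pre-defined time points are not defined in the SAP, and the discharge-day entries conflict.
- A percentage at a fixed time point is not biased by omitting samples taken at other times. This is correct. If the CS tables are read strictly by time point, the defect is that no any-value count exists. If item 3 is read as one count across planned visits, that count is incomplete. The remedy is the same.

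The rule also matches the handling of additional MCF and fibrinogen activity samples (SAP 10.3) and unscheduled ECGs (SAP 11.9). Consistency supports it for summaries by time point, not for a count of any CS value.

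**Conclusion.** The point holds in a limited form. In hospitalised Part II events, a CS coagulation value from a sample outside the pre-defined time points is absent from the coagulation summary and CS tables. It can be found only in the listings and, if recorded as an adverse event, in the TEAE tables. A per-event CS count can therefore be understated and cannot be overstated. The documents do not allow an estimate of how much.

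The possible loss is widest for hospitalised children under 6, whose Day 0 post-infusion sample is as required in the visit schedule. This assumes that an as-required entry at a named visit is not a pre-defined time point, which the SAP leaves open. It is a gap in safety presentation worth closing. It is not evidence that a thrombosis signal is hidden.

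**What to change.** 1. In SAP 11.8, limit the exclusion of as-required coagulation samples to the by-time-point summaries, which stay on planned samples.
2. In item 3 and Tables 14.3.4.6.6 to 14.3.4.6.8, add one row per event: any CS value in any post-dose sample up to the safety visit, scheduled or as required. Add the same row to the matching haematology and chemistry tables. Use the treated events in the analysis set as a fixed denominator.
3. State which samples count as pre-defined time points, covering optional visits and as-required entries at a named visit.
4. Reconcile the discharge-day coagulation entries for children under 6: flowcharts 3.4 and 3.5 against the discharge-day schedule in protocol 13.1.2.4 and against protocol 14.5.1.3.

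The cost is SAP wording and one extra row in existing tables. The values are already due to be listed, and no study procedure changes. There is one statistical drawback: longer stays bring more samples and so more chances of a CS value. Show the row by hospitalisation, with the number of samples per event beside it. Reported rates may become slightly less favourable.

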11.9 ECG

Overall ECG evaluations for part I will be analyzed for SAF. ECG measurements - according to the qualitative data categories "normal", "abnormal – not clinically significant", and "abnormal – clinically significant" - will be described by means of "shift-tables" between baseline and each of the planned post-baseline visits. 'Baseline' visit is the time point of pre-dose measurement at screening within the PK period. ECG at screening for part II and unscheduled measurements will only be provided in the listings.

11.10 Physical examination

Physical examination will include the inspection of general appearance, skin, neck (including thyroid), eyes, ears, nose, throat, heart, lungs, abdomen, lymph nodes, extremities, musculoskeletal and nervous system.

Number and percentages of patients for each category ("normal", "abnormal – not clinically significant", and "abnormal – clinically significant") for part I and on event level from part II, will be generated per inspected organ (plus 'other') for pre-dose and overall.

The overall assessment per inspected organ number and percentage of patients/events will be presented for the categories

- NORMAL, defined as patients/events without any abnormal post baseline evaluation,
- ABNORMAL NOT CS, defined as patients/events with at least one abnormal not clinically significant post baseline evaluation, and
- ABNORMAL CS, defined as patients/events with at least one abnormal clinically significant post baseline evaluation.

'Baseline' visit is the time point of pre-dose measurement within each observation period of the indication/event.

Shift tables comparing baseline visit and Day 49 visit will also be produced for part I and on event level from part II. Values that are identified by the investigator as being clinically significant will also be shown in an additional data listing.

12 Software

If not stated otherwise, the data will be analyzed using SAS Version 9.4 or higher.

13 Abbreviations

AE	Adverse Event
APE	All Patients Enrolled Set
aPTT	Activated partial Thromboplastin Time
ATC	Anatomical Therapeutical Chemical
BW	Body Weight
°C	Degrees Centigrade
cf.	confer
CHMP	Committee for Medicinal Products for Human Use
cm	Centimetre
COA	Certificate Of Analysis
CRO	Contract Research Organization
CS	Clinically Significant
BDRM	Blind Data Review Meeting
ECG	Electrocardiogram
e.g.	For example
EMA	European Medicines Agency
FAS	Full analysis set
F1+2	Prothrombin Fragment 1 and 2
FiAc	Fibrinogen activity
FiAg	Fibrinogen antigen
FU	Follow-up
g	Gram
h	Hour
ICF	Informed Consent Form
ICH	International Council for Harmonization
i.e.	That is
IMP	International Medicinal Product
INR	International Normalized Ratio
IRR	Infusion Related Reaction
IV	Intravenous
kg	Kilogram
L	Liter
lb	Pound
max	Maximum
MCF	Maximum Clot Firmness
MedDRA	Medical Dictionary for Regulatory Activities
mg	Miligram
min	Minimum
min.	Minute
mL	Mililiter
mm	Millimetre

mmHg	millimeters of mercury
NTEAE	Not Treatment Emergent Adverse Event
ODP	On-Demand Prophylaxis

15.1 Table of Content of TLF numbers, titles, and analysis populations

Table	Number	Table Name
Patient Accounting and Disposition		
Patient Accounting		
Table	14.1.1.1.1	Analysis Set: Frequencies and Percentages of Patients – APE I
Table	14.1.1.1.2	Analysis Set: Frequencies and Percentages of Children < 6 years – APE I
Table	14.1.1.1.3	Analysis Set: Frequencies and Percentages of All Patients Enrolled – APE II
Table	14.1.1.1.4	Analysis Set: Frequencies and Percentages of All Children < 6 years Enrolled – APE II
Table	14.1.1.1.5	Analysis Set: Frequencies and Percentages of Patients – SAF II
Table	14.1.1.1.6	Analysis Set: Frequencies and Percentages of Children < 6 years – SAF II
Table	14.1.1.1.7	Analysis Set: Frequencies and Percentages of Bleeding Events – FBE
Table	14.1.1.1.8	Analysis Set: Frequencies and Percentages of Bleeding Events of Children < 6 years – FBE
Table	14.1.1.1.9	Analysis Set: Frequencies and Percentages of Bleeding Events – PPBE
Table	14.1.1.1.10	Analysis Set: Frequencies and Percentages of Bleeding Events of Children < 6 years – PPBE
Disposition		
Table	14.1.1.2.1	Disposition: Frequencies and Percentages of Patients by Country (Worldwide) – APE I and II
Table	14.1.1.2.2	Disposition: Frequencies and Percentages of Patients by Country (EEA) – APE I and II
Table	14.1.1.2.3	Disposition: Frequencies and Percentages of Patients by Age Classification according to EudraCT – APE I and II
Table	14.1.1.2.4	Disposition: Frequencies and Percentages of Patients by Age Group and Overall – APE I
Table	14.1.1.2.5	Disposition: Frequencies and Percentages of Patients by Age Group and Overall – SAF I
Table	14.1.1.2.6	Disposition: Frequencies and Percentages of Patients by Age Group and Overall – APE II
Table	14.1.1.2.7	Disposition: Frequencies and Percentages of Patients by Age Group and Overall – SAF II
Table	14.1.1.2.8	Disposition: Frequencies and Descriptive Statistics of Bleeding Events by Age Group and Overall – FBE
Table	14.1.1.2.9	Disposition: Frequencies and Descriptive Statistics of Bleeding Events of Children < 6 years – FBE
Table	14.1.1.2.10	Disposition: Frequencies and Descriptive Statistics of Bleeding Events by Age Group and Overall – PPBE
Table	14.1.1.2.11.	Disposition: Frequencies and Descriptive Statistics of Bleeding Events of Children < 6 years – PPBE
Listing	16.2.1	Disposition: Informed Consent and Eligibility – APE I and II
Listing	16.2.2	Disposition: Completed and Discontinued Patients – SAF I

Listing	16.2.3	Disposition: Completed and Discontinued Patients – SAF II
Listing	16.2.4	Disposition: Patients Registration – APE I
Listing	16.2.5	Disposition: Patients Registration – APE II
Listing	16.2.6	Disposition: Patient visits – APE I
Listing	16.2.7	Disposition: Patient visits – APE II
Listing	16.2.8	Disposition: Patients and Bleeding Events – FBE
Listing	16.2.9	Disposition: Number of Bleeding Events per Patient – FBE
Listing	16.2.10	Disposition: Number of Bleeding Events per Patient – PPBE
Listing	16.2.11	Disposition: Age group by study population and part – APE I and II
Protocol Deviations		
Table	14.1.1.3.1	Protocol Deviations: Frequencies and Percentages of Patients – SAF I
Table	14.1.1.3.2	Protocol Deviations: Frequencies and Percentages of Patients – SAF II
Table	14.1.1.3.3	Protocol Deviations: Frequencies and Percentages of Bleeding Events – FBE
Table	14.1.1.3.4	Protocol Deviations: Frequencies and Percentages of Patients – FAS I
Table	14.1.1.3.5	Protocol Deviations: Frequencies and Percentages of Patients – FAS II
Listing	16.3.1	Patient Accounting: Analysis Set and Protocol Deviations – APE I
Listing	16.3.2	Patient Accounting: Analysis Set and Protocol Deviations – APE II
Listing	16.3.3	Bleeding Event Accounting: Analysis Set and Protocol Deviations – FBE
Demographics and Background Characteristics		
Demographics		
Table	14.1.2.1.1	Demographic Characteristics: Summary Statistics by Age Group – SAF I
Table	14.1.2.1.2	Demographic Characteristics: Summary Statistics by Children < 6 years – SAF I
Table	14.1.2.1.3	Demographic Characteristics: Summary Statistics by Age Group – SAF II
Table	14.1.2.1.4	Demographic Characteristics: Summary Statistics by Children < 6 years – SAF II
Table	14.1.2.2.1	Demographic Characteristics: Age at Event Treatments by Type of Event (ODP or ODT) – FBE
Table	14.1.2.2.2	Demographic Characteristics: Age at Event Treatments by Type of Event (ODP or ODT) by Children < 6 years – FBE
Listing	16.4.1	Demographic and Baseline Characteristics – SAF I
Listing	16.4.2	Demographic and Baseline Characteristics – SAF II
Listing	16.4.3	Alcohol Consumption and Smoking History – SAF I

Listing	16.4.4	Alcohol Consumption and Smoking History – SAF II
Medical History		
Table	14.1.3.1.1	Previous Medical Conditions: Frequencies and Percentages by SOC and Preferred Term (within each SOC) – SAF I
Table	14.1.3.1.2	Previous Medical Conditions: Frequencies and Percentages by SOC and Preferred Term (within each SOC) – SAF II
Table	14.1.3.2.1	Concomitant Medical Conditions: Frequencies and Percentages by SOC and Preferred Term – SAF I
Table	14.1.3.2.2	Concomitant Medical Conditions: Frequencies and Percentages by SOC and Preferred Term – SAF II
Listing	16.5.1	Medical Conditions - Previous and Concomitant Medical History – SAF I
Listing	16.5.2	Medical Conditions - Previous and Concomitant Medical History – SAF II
Table	14.1.3.3.1	Bleeding History: Summary Statistics for Number of Bleedings and Annual Bleeding Rate – SAF I
Table	14.1.3.3.2	Bleeding History: Summary Statistics for Number of Bleedings and Annual Bleeding Rate – SAF II
Listing	16.5.3	Historical Bleeding due to surgery – SAF I
Listing	16.5.4	Historical Bleeding due to surgery – SAF II
Listing	16.5.5	Number of Historical Bleedings and Annual Bleeding Rate – SAF I
Listing	16.5.6	Number of Historical Bleedings and Annual Bleeding Rate – SAF II
Listing	16.5.7	Bleeding History – SAF I
Listing	16.5.8	Bleeding History – SAF II
Listing	16.5.9	Previous and Concomitant Medication – SAF I
Listing	16.5.10	Previous and Concomitant Medication – SAF II
Listing	16.5.11	Immunoglobulin E – SAF I
Exposure and Compliance		
Dosage		
Table	14.1.4.1.1	Study Medication Dosage: Summary Statistics – SAF I
Table	14.1.4.1.2	Study Medication Dosage: Summary Statistics – FAS I
Table	14.1.4.1.3	Study Medication Dosage: Summary Statistics – PPI
Table	14.1.4.1.4	Study Medication Dosage: Summary Statistics – PK
Listing	16.6.1	Study Medication Dosage: Exposure and Compliance – SAF I
Table	14.1.4.1.5	Study Medication Dosage: Summary Statistics by Type of Treatment (on Event Level) and Degree of Event – FBE
Table	14.1.4.1.6	Study Medication Dosage: Summary Statistics by Type of Treatment (on Event Level) and Degree of Event – PPBE
Table	14.1.4.1.7	Study Medication Dosage: Summary Statistics by Time of Administration (pre, intra, postoperative) for Treated Surgeries – FBE

Table	14.1.4.1.8	Study Medication Dosage: Frequencies and Percentages of Bleeding Events by Number of Infusions – FBE
Listing	16.6.2	Study Medication Dosage: Exposure and Compliance – FBE
Treatment Duration		
Table	14.1.4.2.1	Treatment Duration and Infusion Rates: Summary Statistics – SAF I
Table	14.1.4.2.2	Treatment Duration and Infusion Rates: Summary Statistics – FAS I
Table	14.1.4.2.3	Treatment Duration and Infusion Rates: Summary Statistics – PP I
Table	14.1.4.2.4	Treatment Duration and Infusion Rates: Summary Statistics – PK
Table	14.1.4.2.5	Treatment Duration and Infusion Rates: Summary Statistics (on Event Level) – FBE
Table	14.1.4.2.6	Treatment Duration and Infusion Rates: Summary Statistics (on Event Level) – PPBE
Table	14.1.4.3.1	Infusion Rates Changes and Infusion Interruption: Frequencies and Percentages of Patients – SAF I
Table	14.1.4.3.2	Infusion Rates Changes and Infusion Interruption: Frequencies and Percentages of Patients – FAS I
Table	14.1.4.3.3	Infusion Rates Changes and Infusion Interruption: Frequencies and Percentages of Patients – PP I
Table	14.1.4.3.4	Infusion Rates Changes and Infusion Interruption: Frequencies and Percentages of Patients – PK
Table	14.1.4.3.5	Infusion Rates Changes and Infusion Interruption: Frequencies and Percentages of Events – FBE
Table	14.1.4.3.6	Infusion Rates Changes and Infusion Interruption: Frequencies and Percentages of Events – PPBE
Listing	16.6.3	Treatment duration and infusion rates – SAF I
Listing	16.6.4	Treatment duration and infusion rates – FBE
Previous and Concomitant Therapies		
Table	14.1.5.1.1	Previous Medication or Treatment (ATC Level 2): Frequencies and Percentages of Patients – SAF I
Table	14.1.5.1.2	Previous Medication or Treatment (ATC Level 2): Frequencies and Percentages of Patients – SAF II
Table	14.1.5.1.3	Concomitant Medication or Treatment (ATC Level 2): Frequencies and Percentages of Patients – SAF I
Table	14.1.5.1.4	Concomitant Medication or Treatment (ATC Level 2): Frequencies and Percentages of Patients – SAF II
Efficacy data		
Primary endpoint analyses		
Table	14.2.1.1.1	Fibrinogen Antigen (g/L) – Descriptive Statistics of Changes from Predosing by Time Point and Age Group – SAF I
Table	14.2.1.1.2	Fibrinogen Antigen (g/L) – Descriptive Statistics of Changes from Predosing by Time Point and Age Group – FAS I
Table	14.2.1.1.3	Fibrinogen Antigen (g/L) – Descriptive Statistics of Changes from Predosing by Time Point and Age Group – PP I
Table	14.2.1.1.4	Fibrinogen Antigen (g/L) – Descriptive Statistics of Changes from Predosing by Time Point and Age Group – PK
Listing	16.7.1	Primary Endpoint Analysis – Fibrinogen Antigen (g/L) – SAF I

Secondary endpoint analyses of part I		
Table	14.2.1.2.1	Maximum Clot Firmness – Statistics of Changes from Predosing by Time Point and Age Group – SAF I
Table	14.2.1.2.2	Maximum Clot Firmness – Statistics of Changes from Predosing by Time Point and Age Group – FAS I
Table	14.2.1.2.3	Maximum Clot Firmness – Statistics of Changes from Predosing by Time Point and Age Group – PP I
Table	14.2.1.2.4	Maximum Clot Firmness Predose – Correlation Statistics with Fibrinogen Activity by Time Point and Age Group – SAF I
Table	14.2.1.2.5	Maximum Clot Firmness Predose – Correlation Statistics with Fibrinogen Activity by Time Point and Age Group – FAS I
Table	14.2.1.2.6	Maximum Clot Firmness Predose – Correlation Statistics with Fibrinogen Activity by Time Point and Age Group – PP I
Figure	14.2.1.2.7	Maximum Clot Firmness – Whisker Box Plot by Time Point – SAF I
Table	14.2.1.3.1	Fibrinogen Activity (g/L) – Descriptive Statistics of Changes from Predosing by Time Point and Age Group – SAF I
Table	14.2.1.3.2	Fibrinogen Activity (g/L) – Descriptive Statistics of Changes from Predosing by Time Point and Age Group – FAS I
Table	14.2.1.3.3	Fibrinogen Activity (g/L) – Descriptive Statistics of Changes from Predosing by Time Point and Age Group – PP I
Table	14.2.1.3.4	Fibrinogen Activity (g/L) – Descriptive Statistics of Changes from Predosing by Time Point and Age Group – PK
Secondary endpoint analyses of part II		
Table	14.2.2.1.1	Overall Haemostatic Response on Event Level – Frequency and Percentage Statistics for all Events – FBE
Table	14.2.2.1.2	Overall Haemostatic Response on Event Level – Frequency and Percentage Statistics for all Events – PPBE
Table	14.2.2.1.3	Overall Haemostatic Response on Event Level – Frequency Statistics for ODP by Degree of Event and Overall – FBE
Table	14.2.2.1.4	Overall Haemostatic Response on Event Level – Frequency Statistics for ODP by Degree of Event and Overall – PPBE
Table	14.2.2.1.5	Overall Haemostatic Response on Event Level – Frequency Statistics for ODT by Degree of Event and Overall – FBE
Table	14.2.2.1.6	Overall Haemostatic Response on Event Level – Frequency Statistics for ODT by Degree of Event and Overall – PPBE
Figure	14.2.2.1.7	Overall Haemostatic Response on Event Level – All Events: Pie Chart of Investigator Assessments – FBE
Figure	14.2.2.1.8	Overall Haemostatic Response on Event Level – All Events: Pie Chart of Investigator Assessments – PPBE
Figure	14.2.2.1.9	Overall Haemostatic Response on Event Level – All Events by Age Group: Pie Chart of Investigator Assessments – FBE
Figure	14.2.2.1.10	Overall Haemostatic Response on Event Level – All Events by Age Group: Pie Chart of Investigator Assessments – PPBE
Figure	14.2.2.1.11	Overall Haemostatic Response on Event Level – by Type (ODP or ODT): Pie Chart of Investigator Assessments – FBE
Figure	14.2.2.1.12	Overall Haemostatic Response on Event Level – by Type (ODP or ODT): Pie Chart of Investigator Assessments – PPBE
Figure	14.2.2.1.13	Overall Haemostatic Response on Event Level – by Degree of Event: Pie Chart of Investigator Assessments – FBE
Figure	14.2.2.1.14	Overall Haemostatic Response on Event Level – by Degree of Event: Pie Chart of Investigator Assessments – PPBE
Table	14.2.2.1.15	Summary of Overall Haemostatic Response of the patients by number of events – FBE
Table	14.2.2.1.16	Summary of Overall Haemostatic Response of the patients by number of events – PPBE

Figure	14.2.2.1.17	Overall Haemostatic Response on Event Level – Mean response by event number – FBE
Figure	14.2.2.1.18	Overall Haemostatic Response on Event Level – Mean response by event number – PPBE
Figure	14.2.2.1.19	Overall Haemostatic Response on Event Level - Line plot of haemostatic response by patient and event number – FBE
Figure	14.2.2.1.20	Overall Haemostatic Response on Event Level - Line plot of haemostatic response by patient and event number – PPBE
Listing	16.8.1	Secondary Endpoint Analysis – Overall Haemostatic Response, Total of Loss of Blood, and Wound Healing – FBE
Table	14.2.2.2.1	Administration of Other FCPs on Event Level – Overall Summary Statistics for all Events – FBE
Table	14.2.2.2.2	Administration of Other FCPs on Event Level – Overall Summary Statistics for all Events – PPBE
Table	14.2.2.2.3	Administration of Other FCPs on Event Level – Administration Frequency Statistics for all Events – FBE
Table	14.2.2.2.4	Administration of Other FCPs on Event Level – Administration Frequency Statistics for all Events – PPBE
Table	14.2.2.3.1	Administration of Other TPs on Event Level – Overall Summary Statistics for all Events – FBE
Table	14.2.2.3.2	Administration of Other TPs on Event Level – Overall Summary Statistics for all Events – PPBE
Table	14.2.2.3.3	Administration of Other TPs on Event Level – Administration Frequency Statistics for all Events – FBE
Table	14.2.2.3.4	Administration of Other TPs on Event Level – Administration Frequency Statistics for all Events – PPBE
Listing	16.8.2	Secondary Endpoint Analyses – Administration of Other FCPs and TPs – SAF II
Table	14.2.2.4.1	BT524 Consumption/Dosing on Event Level: Descriptive Statistics Overall and per Infusion for Treated Surgeries – FBE
Table	14.2.2.4.2	BT524 Consumption/Dosing on Event Level: Descriptive Statistics Overall and per Infusion for Treated Surgeries – PPBE
Table	14.2.2.5.1	Wound Healing on Event Level: Frequency Statistics for all Events by Degree of Event – FBE
Table	14.2.2.5.2	Wound Healing on Event Level: Frequency Statistics for all Events by Degree of Event – PPBE
Table	14.2.2.5.3	Wound Healing on Event Level: Frequency Statistics for ODP by Degree of Event and Overall – FBE
Table	14.2.2.5.4	Wound Healing on Event Level: Frequency Statistics for ODP by Degree of Event and Overall – PPBE
Table	14.2.2.5.5	Wound Healing on Event Level: Frequency Statistics for ODT by Degree of Event and Overall – FBE
Table	14.2.2.5.6	Wound Healing on Event Level: Frequency Statistics for ODT by Degree of Event and Overall – PPBE
Table	14.2.2.6.1	Maximum Clot Firmness on Event Level by Age Group: Statistics of Changes from Predosing – FBE
Table	14.2.2.6.2	Maximum Clot Firmness on Event Level by Age Group: Statistics of Changes from Predosing – PPBE
Table	14.2.2.6.3	Maximum Clot Firmness on Event Level by Age Group: Statistics of Changes from Predosing for ODP by Degree of Event and Overall – FBE
Table	14.2.2.6.4	Maximum Clot Firmness on Event Level by Age Group: Statistics of Changes from Predosing for ODP by Degree of Event and Overall – PPBE

Table	14.2.2.6.5	Maximum Clot Firmness on Event Level by Age Group: Statistics of Changes from Predosing for ODT by Degree of Event and Overall – FBE
Table	14.2.2.6.6	Maximum Clot Firmness on Event Level by Age Group: Statistics of Changes from Predosing for ODT by Degree of Event and Overall – PPBE
Table	14.2.2.6.7	Maximum Clot Firmness on Event Level by Age Group: Correlation Statistics with Fibrinogen Activity by Time Point – FBE
Table	14.2.2.6.8	Maximum Clot Firmness on Event Level by Age Group: Correlation Statistics with Fibrinogen Activity by Time Point – PPBE
Figure	14.2.2.6.9	Maximum Clot Firmness on Event Level by Age Group: Whisker Box Plot for all Events – FBE
Figure	14.2.2.6.10	Maximum Clot Firmness on Event Level by Age Group: Whisker Box Plot for all Events – PPBE
Figure	14.2.2.6.11	Maximum Clot Firmness on Event Level by Age Group: Whisker Box Plot for ODP by Degree of Event and Overall – FBE
Figure	14.2.2.6.12	Maximum Clot Firmness on Event Level by Age Group: Whisker Box Plot for ODP by Degree of Event and Overall – PPBE
Figure	14.2.2.6.13	Maximum Clot Firmness on Event Level by Age Group: Whisker Box Plot for ODT by Degree of Event and Overall – FBE
Figure	14.2.2.6.14	Maximum Clot Firmness on Event Level by Age Group: Whisker Box Plot for ODT by Degree of Event and Overall – PPBE
Listing	16.8.3	Secondary Endpoint Analysis Maximum Clot Firmness – SAF I and FBE
Table	14.2.2.7.1	Fibrinogen Activity (g/L) on Event Level by Age Group: Descriptive Statistics of Changes from Predosing for all Events – FBE
Table	14.2.2.7.2	Fibrinogen Activity (g/L) on Event Level by Age Group: Descriptive Statistics of Changes from Predosing for all Events – PPBE
Table	14.2.2.7.3	Fibrinogen Activity (g/L) on Event Level by Age Group: Descriptive Statistics of Changes from Predosing for ODP by Degree of Event and Overall – FBE
Table	14.2.2.7.4	Fibrinogen Activity (g/L) on Event Level by Age Group: Descriptive Statistics of Changes from Predosing for ODP by Degree of Event and Overall – PPBE
Table	14.2.2.7.5	Fibrinogen Activity (g/L) on Event Level by Age Group: Descriptive Statistics of Changes from Predosing for ODT by Degree of Event and Overall – FBE
Table	14.2.2.7.6	Fibrinogen Activity (g/L) on Event Level by Age Group: Descriptive Statistics of Changes from Predosing for ODT by Degree of Event and Overall – PPBE
Listing	16.8.4	Secondary Endpoint Analysis: Fibrinogen Activity – SAF I and FBE
Table	14.2.2.8.1	Fibrinogen Antigen (g/L): Descriptive Statistics of Screening Values by Age Group – SAF II
Table	14.2.2.8.2	Fibrinogen Antigen (g/L): Descriptive Statistics of Screening Values by Age Group – FAS II
Table	14.2.2.8.3	Fibrinogen Antigen (g/L): Descriptive Statistics of Screening Values by Age Group – PP II
Listing	16.8.5	Fibrinogen Antigen – SAF II
Table	14.2.2.9.1	Total Loss of Blood Classifications on Event Level: Frequency Statistics for Treated Surgeries – FBE
Table	14.2.2.9.2	Total Loss of Blood Classifications on Event Level: Frequency Statistics for Treated Surgeries – PPBE

Safety Data		
Exposure and Compliance		
Adverse Events		
Table	14.3.1.1.1	Adverse Events: Overview of Frequencies and Percentages of Patients – APE I and II
Table	14.3.1.1.2	Adverse Events: Overall by Age Group: Overview of Frequencies and Percentages of Patients – APE I and II
Table	14.3.1.1.3	Adverse Events by Age Group: Overview of Frequencies and Percentages of Patients – APE I
Table	14.3.1.1.4	Adverse Events by Age Group: Overview of Frequencies and Percentages of Patients – APE II
